
Interventions
	
Endovascular Thrombectomy: Patients randomized to endovascular thrombectomy, will be treated with thrombectomy stent-retrievers and/or aspiration devices currently cleared by the FDA. The choice of thrombectomy method, primary approach/technique, whether primary aspiration or primary stent-retriever with or without aspiration, will be left up to the interventionalist, with any of the FDA-approved devices approved in the study protocol or a combination of them (Appendix C). Standard medical therapy, based on current AHA guidelines, will also be provided for all patients.
 
Medical Management: Patients randomized to medical management only will receive standard medical therapy based on current AHA guidelines. Patients will receive IV thrombolytic therapy available for use according to practice guidelines if presented within the first 3 hours from last known well and meeting other FDA label criteria, or up to 4.5 hours from last-seen-normal and meeting other AHA guidelines. No procedures or tests required by the protocol will delay fastest possible delivery of thrombolytic therapy to potentially eligible subjects. For thrombolysis treated patients, the sites' post-thrombolysis protocol will be followed. The non-thrombolysis treated patients will be treated with aspirin, 325 mg on Day 1, and 81-325 mg/day (investigator's preference) on day 2-5, unless an indication for early anticoagulation is present (as determined by the patient's attending physician). All patients will receive standard DVT prevention therapy.

Assessment and Visits
	
Clinical assessments will be done at baseline, 24-hours after randomization, day 5-7 or hospital discharge (whichever is earlier), 30 days, and 90 days:
 
 1. Baseline: demographics and medical history, CT/CTA/CTP/MRP imaging, lab work, hourly blood pressure, NIHSS, mRS 2. 24 hours (+/- 6 hrs): hourly blood pressure, NIHSS 3. 24 hour – 7 days post-procedure imaging (MRI or CT if MRI not feasible) 4. Day 5-7 or discharge (whichever is earlier): NIHSS, mRS 5. Day 30 (+/- 15 days): mRS 6. Day 90 (+/- 15 days): mRS, Neuro-QoL

Protocol

1. Scientific Background

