Considering a prior assumption that the EVT effect is largest in the patients with good imaging profile and treated within the shortest time window, we assume that the highest effect of EVT will be observed in G1A. Then the effects get decreased gradually in G1B, G2A, G2B, G3A, and the lowest effect will be observed in G3B. According to this adaptive design, when a most promising subgroup needs to be selected at the time of interim (or final) analysis, we will compare the GLR statistic among five cumulative groups, that is, G1A, G1A+G1B (i.e., Group 1), G1A+G1B+G2A, G1A+G1B+G2A+G2B (i.e., Group 1+Group 2), and G1A+G1B+G2A+G2B+G3A.

Primary analysis: The primary endpoint is the distribution of scores on the modified Rankin Scale (mRS) at day 90. The null hypothesis will be tested at the interim and final analysis using a normal approximation of the Wilcoxon-Mann-Whitney test (the GLR test). The principle of the intention to treat will be applied for the primary analysis. An additional analysis of the primary endpoint will be the same rank-based analysis comparing the 90-day mRs distribution between treatment groups while stratifying for prognostically important covariates. We will use the Generalized Cochran-Mantel-Haenszel test (CMH) to evaluate whether there is a uniform shift on the mRS distribution from one group to the other after stratification. The CMH test will be stratified by these variables used in the covariate adaptive randomization. For age, NIHSS, treatment time window, and CTP core volume, we will consider them as continuous variables in this adjusted analysis.

Power and sample size considerations Based on prior reported data, the following distributions were projected on the mRS at 90 days in EVT and MM groups for SELECT 2 in the overall population.

	mRS at day 90							Total
	0	1	2	3	4	5	6	
Endovascular group	4%	8%	12%	16%	19%	13%	28%	100%
Medical group	1%	4%	9%	14%	19%	10%	43%	100%

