6.5. Missing Data/Lost to Follow-up (LTFU)

All effort is put forth to ensure near complete follow-up, in particular with the assessment of the primary outcome (mRS at 90 days), death (mRS=6), and stroke recurrence. If the primary outcome (mRS at 90 days) cannot be assessed in the clinic, it will instead be obtained by phone using a structured interview. If the subject's mRS cannot be obtained in clinic or by phone within the window of 60 to 120 days from randomization, we will use multiple imputation method to impute 90-day mRS. Specifically, using the data from patients with available 90-day mRS, we will build ordinal logistic regression based on patient baseline features and prior mRS scores to impute 90-day mRS.

7. SELECT 2 Timetable

8. Risk Analysis

Description and analysis of all increased risks to the research subjects:

Potential complications of MRI scan include localized twitching sensation due to the magnetic field changes during the scan, anxiety due to claustrophobia and allergic reaction to the contrast agent. The allergic reaction may include headache, nausea, rash, hives, nasal congestion, sneezing, itching or swelling. If a severe reaction occurs, swelling of the throat, chest tightness, or a marked drop in blood pressure may occur. In addition, pain, bleeding, bruising, coldness or inflammation at the injection site may occur. Precautions will be taken for early detection and rapid treatment if such reactions occur.

Potential complications of CT scan include radiation exposure and allergic reaction to CT contrast agents. The iodinated contrast administration may also result in transient and rarely permanent renal failure due to nephrotoxicity.

Radiation doses:

Combined scanning with comprehensive stroke imaging, which includes a non-contrast head CT scan, perfusion imaging, and CT angiography of the cervicocranial vessels starting at the aortic arch results in a dose of approximately 7-10 mSv (Diekmann et al. 2010). According to the National Council on Radiation Protection and Measurement, the average annual radiation dose per person in the U.S. is 620 millirem (6.2 milliSieverts).

Reactions to contrast agents:

Mild

Nausea, Vomiting, Headache, Cough, Nasal stuffiness, altered taste, Flushing, Itching, Rash, Hives, Sweats, Swelling of eyes or face

Moderate

Mild hypotension, Tachycardia or Bradycardia, Bronchospasm, Wheezing, Dyspnea, Laryngeal edema, Generalized or diffuse erythema

Severe

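### The imputation model for missing 90-day mRS does not name randomized arm, so followed as written it attenuates the primary effect, by an amount likely to be small

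*Combined protocol and SAP*

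**What the plan says.** Section 6.5 is the only description of the imputation model. Imputation applies when no mRS is obtained in clinic or by telephone "within the window of 60 to 120 days from randomization, we will use multiple imputation method to impute 90-day mRS". The fit rests on patients whose 90-day score was observed, and the predictors are stated as follows: "we will build ordinal logistic regression based on patient baseline features and prior mRS scores to impute 90-day mRS". That sentence is introduced as the specific form of the method, so its predictor list reads as the definition. Arm is not in the list, and fitting by arm is not mentioned. The covariates, the visits that count as earlier mRS, and the number of imputations are also not listed.

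The schedule provides two mRS assessments between randomization and day 90: "Day 5-7 or discharge (whichever is earlier): NIHSS, mRS" and "Day 30 (+/- 15 days): mRS". Section 6.5 treats death as mRS 6 and gives no expected missing rate, saying only that "All effort is put forth to ensure near complete follow-up".

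On the primary comparison, section 6.1 says: "The principle of the intention to treat will be applied for the primary analysis". The test is a Wilcoxon-Mann-Whitney comparison of the arms on the 90-day mRS. Appendix B uses the same statistic within cumulative groups built from G1A to G3B to choose a subgroup.

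**The concern.** An imputation model should contain the variables that the analysis compares. Here the analysis compares the arms, and arm is the variable not named. Two patients from different arms who match on baseline features and earlier mRS would draw from one common distribution. The part of the treatment effect that appears after the last observed mRS is therefore removed for every imputed patient. Under a true benefit the bias runs one way, toward the null. It grows with the share of patients imputed and shrinks with the amount of effect that the earlier scores already carry. It matters most for patients lost before the day-30 visit.

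**Working it through.** **1. Reproduce the plan's figure.** Inputs are the projected mRS 0-6 distributions in section 6.1: thrombectomy 4/8/12/16/19/13/28%, medical 1/4/9/14/19/10/43%. Let P be the probability that a thrombectomy patient has the better score, with ties counted half.
- P = 0.59375, so P-0.5 = 0.094.
- Tie factor T = 1 - Σ(mean proportion)³ = 0.942.
- N = T(1.960+1.282)²/[3(P-0.5)²] = 375.4, i.e. 376. This matches the stated 376 (188 per arm).

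The documents give no figure for the effect of imputation. The missing share f and the correlation ρ between the earlier and the 90-day score are therefore assumptions below.

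**2. Upper bound: no usable post-randomization mRS.** Imputed patients show no arm difference, so the effect is multiplied by (1-f).
- f = 5%: 0.09375 × 0.95 = 0.089.
- f = 10%: 0.09375 × 0.90 = 0.084. In standardized units, 0.34 × 0.90 = 0.306.

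Table 3 gives adaptive power of 81.1% at 0.30 and 86.0% at 0.32. Linear interpolation at 0.306 gives 81.1 + 0.3 × 4.9 = 82.6%, against about 91% at 0.34.

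**3. Earlier post-randomization mRS available.** Assume the same arm shift d at the earlier visit and at day 90. Omitting arm keeps a fraction b = (ρ + d²/4)/(1 + d²/4) of the effect in imputed patients, and the overall effect is d[1 - f(1-b)]. For d = 0.34, d²/4 = 0.0289. With ρ = 0.8, b = 0.8289/1.0289 = 0.806.

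| Missing | ρ = 0.5 | ρ = 0.8 | ρ = 0.9 |
|---|---|---|---|
| 2% | 0.337 | 0.339 | 0.339 |
| 5% | 0.332 | 0.337 | 0.338 |
| 10% | 0.324 | 0.333 | 0.337 |

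At 5% and ρ = 0.8 (0.3367 unrounded), interpolating between 86.0% at 0.32 and about 91% at 0.34 gives 86.0 + (0.0167/0.02) × 5 = 90.2%, a loss of under one point.

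**4. Multiple-imputation simulation.** This used the projected distributions, 188 per arm in a fixed design, 10 imputations, 1,000 trials per row, ρ = 0.8, and values missing completely at random. Donors were drawn within bands of earlier mRS as a stand-in for the ordinal regression. With complete data, P-0.5 = 0.094 and power = 0.907.

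| Missing | Predictors | P-0.5, no arm | P-0.5, arm added | Power, no arm | Power, arm added |
|---|---|---|---|---|---|
| 5% | no earlier mRS | 0.087 | 0.095 | 0.861 | 0.891 |
| 5% | earlier mRS | 0.092 | 0.095 | 0.892 | 0.910 |
| 10% | no earlier mRS | 0.085 | 0.094 | 0.824 | 0.879 |
| 10% | earlier mRS | 0.091 | 0.094 | 0.886 | 0.891 |

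Among imputed patients, P-0.5 was about zero without an earlier mRS and about 0.069 with one, so roughly a quarter of the effect was lost. Adding arm brought it back to about 0.093. Simulation error in power is about one point, so the power differences in the earlier-mRS rows are not clearly resolved. In the other rows, the part due to omitting arm is 3.0 points (0.891 - 0.861) and 5.5 points (0.879 - 0.824). The rest of the fall from 0.907 is lost information, which no imputation model recovers.

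**The case against.** The strongest reply is that section 6.5 is a one-sentence outline that is silent on arm. It does not exclude arm, and a programmer could add it. That is fair as to intent. But the sentence presents itself as the definition of the model, and arm is not ordinarily a patient baseline feature. A prespecified primary analysis should not depend on departing from its written predictor list.

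The second reply concerns size, and most of it stands. A reader might infer that imputed patients show no arm difference at all. The documents do not support that: the model also conditions on earlier mRS, and two such scores are scheduled after randomization. A patient lost after discharge would usually have at least one. Deaths are scored 6 and are not missing. The telephone interview and the wide 60-to-120-day window hold missingness down further. If the missing patients are mostly survivors, less is at stake: leaving mRS 6 out of the projected table gives P-0.5 of about 0.046 (2239.5/(72 × 57) - 0.5).

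A reader might also take the bound of 0.306, with adaptive power in the low 80s, as the expected loss. It needs 10% missing and no usable post-randomization mRS in any of those patients, and nothing in the plan points to that. Nor is there a type I error problem, since the pull is toward no difference.

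A last fair point is that adding a single arm term is not the complete remedy in a design that compares subgroups. The fix allows for this.

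**Conclusion.** The point holds in limited form. As written, the imputation model removes whatever part of the treatment effect is not already carried by the discharge or day-30 mRS, so the primary estimate is attenuated under a true benefit. The direction is the same in every case computed. At an assumed 2-5% missing with a post-randomization mRS available, the loss is very small: about 0.092 against 0.094 at 5%, or 0.337 against 0.34 in standardized units. The bound is 0.306 against 0.34.

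These sizes rest on assumed missing rates, an assumed correlation, values missing completely at random, an arm effect already present in full at the earlier visit, and the reading that the earlier scores include the post-randomization visits. If much of the effect emerges after day 30, the loss moves toward the bound. The adaptive power figures are interpolated from the plan's own results and assume the same missing share at each look. The change is worth making because it removes a one-directional bias from the primary analysis at almost no cost.

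**What to change.** Amend section 6.5, before unblinded outcome data are seen, as follows.
- Name randomized arm as a predictor in the ordinal imputation model, or impute separately by arm.
- Keep the baseline features and earlier mRS. List the baseline covariates, and state that the day 5-7/discharge and day-30 scores are used.
- Include the factors that define G1A to G3B: the ASPECTS/core-volume group and the 0-12 versus 12-24 hour window. Use arm-by-group terms or by-arm fitting where the data allow. Appendix B selects a subgroup on its own Wilcoxon statistic, and a single arm term would impute one common effect in every group and pull the group contrasts toward the average.
- State in advance how sparse groups are handled. With the 6% that section 6.1 assumes for G1B and for G2B, the first interim at 200 patients would have about 12 patients in each (0.06 × 200), too few for separate arm-by-group terms.

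The cost is a slightly larger imputation model and a little more variance. In the simulation, adding arm produced no visible loss of power.

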6.4. Feasibility of enrollment

The study is planning to involve 30 high volume centers with volumes of 150-200 thrombectomies/site/year. Based on SELECT data, roughly 20% of the patients have unfavorable imaging profiles on either CT or CTP, with ~30 patients/site/year eligible to participate in the study. Assuming 50% of the patients consenting to participate in the study and at 30 sites coming onboard in a gradual fashion, the study will complete the enrollment target (560 patients) in nearly 2 years.

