For endovascular patients with Extracranial Occlusions, we will conduct the two-step stopping rules for sICH after we enroll 20 patients in this group and then conduct monitoring after every 10 patients in this group (We expect 10% of patients will have isolated extracranial ICA occlusions, that is, among 280 endovascular patients, around 28 endovascular patients are with extracranial ICA occlusions). Similarly, we assign a weakly informative prior distribution for both π_S^E and π_S^M , that is, a beta distribution with two shape parameters at 0.35 and 0.65, which centers at 0.35 with an effective sample size of 1.

The rule of step 1 for sICH in this group can be pre-determined in the following table.

Find your number of **endovascular patients with Extracranial ICA occlusions** in the left-side column (we provide the table up to 100 patients, but if we enroll more than 100 patients in this group, we will run the algorithm and identify the # of sICHs which will trigger the rule). The step 1 for sICH will be triggered if the number of sICHs is in the range in the right-side column (the range is inclusive):

# of patients with extracranial ICA occlusions	# of sICHs
20	11-20
30	16-30
40	20-40
50	24-50
60	28-60
70	32-70
80	36-80
90	40-90
100	44-100

For mortality,

- 1) **Step 1 for mortality:** check whether the posterior probability that the rate of mortality at Day 90 in one of the endovascular group is $> 40\%$ exceeds the cut-off 0.95. That is, check whether $\Pr\{\pi_m^E > 0.40 \mid \text{data}\} > 0.95$, where the mortality rate in this endovascular group is denoted as π_m^E .

In the event that Step 1 for mortality in one of the endovascular group is triggered, step 2 for mortality in this group will be executed. Otherwise, continue the trial.

- 2) **Step 2 for mortality:** if Step 1 for mortality in one of the endovascular group is triggered, check whether the posterior probability that the mortality rate in this endovascular group is higher than the corresponding medical management by 10% exceeds the cut-off 0.95. That is, check whether $\Pr\{\pi_m^E > \pi_m^M + 10\% \mid \text{data}\} > 0.95$, where the mortality rate in the corresponding medical management group is denoted as π_m^M .

In the event that Step 2 for mortality in one of the endovascular group is triggered, patient enrollment will be placed on hold and a meeting of the DSMB will be conducted to discuss the events and make a determination on the continuation of the trial.

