For endovascular patients with CTP/MRP core volume $\leq 100\text{cc}$, we will conduct the two-step stopping rules for mortality after we enroll 50, 100, 150, 200, and 250 in this group (the maximum number of patients to be enrolled into the endovascular group is 280 and we expect 80% of patients' CTP/MRP core volume will $\leq 100\text{cc}$). We assign a weakly informative prior distribution for both π_m^E and π_m^M , that is, a beta distribution with two shape parameters at 0.4 and 0.6, which centers at 0.4 with an effective sample size of 1.

The rule of step 1 for mortality in this group can be pre-determined in the following table.

Find your number of **patients with CTP/MRP core volume $\leq 100\text{cc}$ in the endovascular group** in the left-side column. The step 1 for mortality will be triggered if the number of deaths is in the range in the right-side column (the range is inclusive):

# of patients with CTP/MRP core volume $\leq 100\text{cc}$ in the endovascular group	# of deaths
50	26-50
100	49-100
150	71-150
200	92-200
250	113-250

For endovascular patients with CTP/MRP core volume $> 100\text{cc}$, we will conduct the two-step stopping rules for mortality after we enroll 20 patients in this group and then conduct monitoring after every 10 patients in this group (We expect 20% of patients' CTP/MRP core volume will $> 100\text{cc}$, that is, among 280 endovascular patients, around 56 endovascular patients

are with CTP/MRP core volume >100cc.). Similarly, we assign a weakly informative prior distribution for both π_m^E and π_m^M , that is, a beta distribution with two shape parameters at 0.4 and 0.6, which centers at 0.4 with an effective sample size of 1.

The rule of step 1 for mortality in this group can be pre-determined in the following table.

Find your number of **endovascular patients with CTP/MRP core volume >100cc** in the left-side column (we provide the table up to 100 patients, but if we enroll more than 100 patients in this group, we will run the algorithm and identify the # of deaths which will trigger the rule). The step 1 for mortality will be triggered if the number of deaths is in the range in the right-side column (the range is inclusive):

# of patients with CTP/MRP core volume >100cc in the endovascular group	# of deaths
20	12-20
30	17-30
40	22-40
50	26-50
60	32-60
70	35-70
80	40-80
90	44-90
100	49-100

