For endovascular patients with Extracranial ICA occlusions, we will conduct the two-step stopping rules for mortality after we enroll 20 patients in this group and then conduct monitoring after every 10 patients in this group (We expect 10% of patients to have isolated extracranial ICA occlusion, that is, among 280 endovascular patients, around 28 endovascular patients are with extracranial ICA occlusions). Similarly, we assign a weakly informative prior

distribution for both π_m^E and π_m^M , that is, a beta distribution with two shape parameters at 0.4 and 0.6, which centers at 0.4 with an effective sample size of 1.

The rule of step 1 for mortality in this group can be pre-determined in the following table.

Find your number of **endovascular patients with Extracranial ICA occlusions** in the left-side column (we provide the table up to 100 patients, but if we enroll more than 100 patients in this group, we will run the algorithm and identify the # of deaths which will trigger the rule). The step 1 for mortality will be triggered if the number of deaths is in the range in the right-side column (the range is inclusive):

# of patients with Extracranial ICA occlusions	# of deaths
20	12-20
30	17-30
40	22-40
50	26-50
60	32-60
70	35-70
80	40-80
90	44-90
100	49-100

These rules only serve as guides and do not substitute for the independent decision-making of the DSMB in the determination of whether the study should be stopped for safety reasons. The decision to stop the study will be made by the DSMB after review of all adverse events based on its own independent decision making. The investigators and the sponsor will not be informed of the interim grouped results.

11. Imaging Core Lab

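### The Day-90 mortality looks are set by enrolment count, but their trigger tables are valid only if every counted patient has a known Day-90 status

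*Combined protocol and SAP*

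**What the plan says.** Section 10, mortality rule, Step 1: "check whether the posterior probability that the rate of mortality at Day 90 in one of the endovascular group is" greater than 40% "exceeds the cut-off 0.95". If Step 1 fires, Step 2 asks whether endovascular mortality exceeds medical-management mortality by 10 points, with the same cut-off. Enrolment is put on hold, and the DSMB meets, only if Step 2 also fires.

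Timing for cores up to 100 cc: "we will conduct the two-step stopping rules for mortality after we enroll 50, 100, 150, 200, and 250 in this group". For cores above 100 cc and for extracranial ICA occlusion, the rule is run "after we enroll 20 patients in this group and then conduct monitoring after every 10 patients in this group". The reader looks up the number of patients in the endovascular group and then applies this: "The step 1 for mortality will be triggered if the number of deaths is in the range in the right-side column".

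The documents state no Day-90 follow-up requirement for these looks and do not say how patients still in follow-up are handled. Two other rules make a useful contrast:
- The sICH rule in Section 10 uses the same enrolment timing, but its endpoint is assessed within 24 hours of randomization.
- The interim and final efficacy analyses in Section 6.1 count only patients who have finished 90 days of follow-up.

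**The concern.** Enrolment timing suits a 24-hour endpoint. For a 90-day endpoint, some patients in the count cannot yet have the outcome. If the table is read at the enrolment count, they enter the denominator while only deaths to date enter the numerator. The observed rate is then biased low, most where recent patients are the largest share of the group, which is at the first looks.

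The first looks matter because a Step 1 non-trigger means the trial continues, and in the group with cores up to 100 cc the next look comes 50 endovascular patients later. Section 1.3 also relies on stringent monitoring of mortality and sICH in explaining why cores above 100 cc were admitted.

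**Working it through.** **1. Reproduce the plan's limits.** The prior is "a beta distribution with two shape parameters at 0.4 and 0.6, which centers at 0.4 with an effective sample size of 1". After x deaths in n patients with known status, the posterior is Beta(0.4 + x, 0.6 + n − x). The limit is the smallest x with Pr(π > 0.40) > 0.95. At n = 50, x = 25 gives 0.920 and x = 26 gives 0.955, so the limit is 26. For n = 100, 150, 200 and 250 the same rule gives 49, 71, 92 and 113. All five match the plan, and all assume n known outcomes.

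**2. Patients still inside 90 days.** Section 10 says "the maximum number of patients to be enrolled into the endovascular group is 280" and expects 80% to have cores up to 100 cc: 280 × 0.80 = 224. Section 6.4 says "the study will complete the enrollment target (560 patients) in nearly 2 years". So 224 / 24 = 9.33 per month, one every 30.44 / 9.33 = 3.26 days, and 90 / 3.26 = 27.6, or about 28 patients inside 90 days at any look. That is 28 of 50 at the first look. Section 6.4 has sites joining gradually, so half the average rate is taken as a low case (an assumption): about 14 of 50.

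**3. Share of deaths already recorded.** A patient followed for t days has a recorded death with probability p × F(t), where p is true Day-90 mortality and F(t) is the share of Day-90 deaths that occur by day t. F is not in the documents. The assumed range runs from deaths uniform over 90 days to 90% of deaths by day 30 (truncated exponential). With even accrual, mean F over the first 50 is 0.71–0.91 at average accrual and 0.85–0.95 at half rate. Expected deaths reach 26 when p = 0.52 / mean F. That is 57%–73% or 55%–61%, against 52% with full follow-up.

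**4. Step 1 trigger probability.** Full follow-up is the binomial tail P(X ≥ limit). At the enrolment count it is the exact Poisson-binomial tail with probabilities p × F(t).

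| Group, look, accrual per month | True mortality | Full follow-up | Enrolment count |
|---|---|---|---|
| ≤100 cc, n = 50, 9.3 | 50% | 0.44 | 0.01–0.21 |
| ≤100 cc, n = 50, 4.7 | 50% | 0.44 | 0.11–0.31 |
| ≤100 cc, n = 50, 9.3 | 60% | 0.90 | 0.10–0.70 |
| ≤100 cc, n = 50, 4.7 | 60% | 0.90 | 0.51–0.81 |
| ≤100 cc, n = 100, 9.3 | 50% | 0.62 | 0.12–0.44 |
| ≤100 cc, n = 150, 9.3 | 50% | 0.77 | 0.33–0.64 |
| ≤100 cc, n = 200, 9.3 | 50% | 0.89 | 0.58–0.81 |
| >100 cc, n = 20, 56/24 = 2.3 | 50% | 0.25 | 0.05–0.15 |
| >100 cc, n = 20, 2.3 | 60% | 0.60 | 0.18–0.42 |

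**5. Step 2.** With the same accrual in both arms, the expected observed difference is mean F times the true difference, while the margin stays at 10 points. At the first look with average accrual, a true 20-point gap appears as about 14 to 18 points (0.71 × 20 to 0.91 × 20). Both steps were simulated at 50 per arm, with deaths uniform or front-loaded (mean 20 days). At 50% versus 30% mortality, both fire in about 20% of trials with full follow-up. At the enrolment count this is about 1–8% at average accrual and 7–14% at half rate.

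**6. Same calendar date, completers only.** At the 50th enrolment 22 patients are complete (limit 13) at average accrual, or 36 (limit 20) at half rate. Step 1 fires with probability 0.26 or 0.31 at 50% mortality, and 0.62 or 0.76 at 60%.

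**The case against.** **The rule is the posterior, and the table is a shortcut for it.** A reader might infer that the plan scores patients still in follow-up as survivors. It does not say so; that is only what a literal reading of the table does. The DSMB statistician could restrict the calculation to completers, and the DSMB charter, attached to the protocol but not among these documents, might say so. This stands as a limit on the claim. It does not supply the missing condition in Section 10.

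**Step 1 alone stops nothing.** A reader might take the fall from 0.44 as a fall in the chance that the trial is paused. That is wrong. With endovascular mortality at 50% and the plan's projected 43% for medical management (Section 6.1), both steps fire in only about 2% of trials at n = 50 even with full follow-up. The loss in holds matters only if the true gap is large.

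**Accrual.** A reader might apply the full-site rate implied by Section 6.4 (30 sites × 30 eligible × 50% = 450 a year, so 450 / 2 × 0.80 = 180 endovascular patients with cores up to 100 cc) and conclude that about 45 of the first 50 are unresolved. The gradual site start makes that rate least plausible at the first look.

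**The full-follow-up comparator comes about 90 days later.** Against completers at the same date, the loss is small or nil if deaths are early: 0.21 versus 0.26, and 0.31 versus 0.31, at 50% mortality. At 60% with early deaths, the enrolment count even does slightly better (0.70 versus 0.62; 0.81 versus 0.76), because completers-only discards known early deaths. With deaths spread evenly the loss is large (0.01 versus 0.26; 0.11 versus 0.31).

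**Other safeguards.** The rules only guide the DSMB, SAEs are reported within 24 hours, and the Medical Safety Monitor reviews them in real time. These soften the consequence.

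**Conclusion.** The point holds as a mismatch between the endpoint, the timing of the looks and the tables. The limits need complete Day-90 status, the looks are set by enrolment, and nothing in the documents connects the two. Used as written, Step 1 and the Step 2 difference are biased toward not triggering.

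The direction of the bias is certain; its size depends on accrual and timing of death. For cores up to 100 cc at n = 50 and 50% true mortality, the Step 1 probability drops from 0.44 to somewhere between 0.01 and 0.31 across the two accrual rates. By n = 200 at average accrual it is 0.58–0.81 against 0.89. The documents do not support saying that the rule is disabled, or that the trial would fail to pause with these probabilities. It should be corrected because a non-trigger at an early look could reassure more than the data allow.

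**What to change.** Keep the enrolment-triggered look dates. In Section 10 and the DSMB charter, state that Steps 1 and 2 are computed, in both arms, on patients whose 90-day window has elapsed and whose Day-90 status is known. Recompute the Step 1 limit for that number with the stated Beta(0.4, 0.6) rule, for example 13 deaths of 22 or 20 of 36. Selecting on elapsed window matters: adding early deaths without the survivors enrolled alongside them would bias the rate upward. Alternatively, specify a time-to-event estimate of Day-90 mortality, which also uses early deaths and avoids the loss of information noted above. Label the printed tables as valid only for n patients with known Day-90 status.

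Simply re-keying the existing tables to completers is less attractive. At average accrual the first look would move to about 50 + 28 = 78 enrolled. The n = 200 look would move to about 228, past the 224 expected endovascular patients with cores up to 100 cc, when no enrolment would be left to hold.

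While the tables are open, check the n = 60 row for cores above 100 cc and for extracranial ICA occlusion: the plan prints 32 deaths, but its rule gives 31 (posterior 0.964).

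The cost is a few sentences, slightly more computation at each look and, for completers only, a smaller n at the first looks.
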